The Expanded Feasibility Study of this protocol is designed to implement the iTBS administration parameters established from the Pilot with a large sample of treatment seeking CD participants. HC participants will be recruited as a comparison group and participate in two days of iTBS (1 active day and 1 sham day of iTBS). Regardless of group, each day of iTBS will include 3 iTBS sessions with at least a 60-minute interval between administrations.

Note that a 3-minute iTBS application is referred to as a SESSION and 3 iTBS sessions is referred to as a DAY of treatment. Therefore, each DAY of iTBS treatment includes 3 iTBS SESSIONS and 10 DAYS of iTBS treatment includes a total of 30 iTBS SESSIONS.

All participants will complete the same battery of characterization instruments.

Participants who successfully complete the iTBS orientation phase (receiving either active or sham iTBS as randomly assigned) will be eligible to participate in iTBS treatment days. CD participants will be scheduled for 10 DAYS of iTBS treatment and receive either active or sham iTBS (assigned randomly prior to orientation). HC participants will be scheduled for 2 DAYS of iTBS and receive 1 DAY of active iTBS (3 active sessions with at least 60 minutes between sessions) and 1 DAY of sham iTBS (3 sham sessions with at least 60 minutes between sessions) with at least 1 week between days. The order of these days will be counterbalanced. Note that 3 sessions of iTBS is well under the minimum number needed to assess efficacy clinically for a treatment effect in depression⁷¹ and has been previously safely carried out in healthy controls^{99, 100, 135}. **These 3 published studies administer iTBS more aggressively than proposed here in healthy controls without adverse events. One study administered 2 iTBS sessions back-to-back in healthy controls without adverse events¹³⁵. Two studies administered 3 iTBS sessions with 15 minutes between sessions in healthy controls without adverse events^{99, 100}.**

B. Goals

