The primary goal is to characterize neurobiological processing of and behavioral responding in cue reactivity, reward processing, executive control, and intrinsic network connectivity differences between HC and CD participants at baseline, during and following iTBS intervention. The Expanded Feasibility Study is powered to assess neuroplastic changes between completers in the CD group who receives active iTBS (N = 30), the CD group who receives sham iTBS (N = 30), and the HC group who receives a within-participant active/sham iTBS manipulation (N = 40). Specifically, we will test for potential neural plasticity over time in the CD cohort and relate any changes to treatment group ongoing substance use (i.e., reductions or maintenance of use). Each CD participant is expected to complete a total of 8 MRI scan sessions across 5 days over a 14-week period 1. Multiple MRI scan sessions will allow for direct comparisons of neural plasticity within participants over time.

C. Aims

1. To characterize neural differences between CD and HC participants at baseline.
2. To determine if iTBS alters networks related to cognitive/affective function by:
 - a. Identifying networks and cognitive/affective functions that change with acute treatment in both HC and CD.
 - b. Identifying networks and cognitive/affective functions that show sustained change (2 weeks after end of treatment) with chronic treatment in CD.
3. To determine if imaging measures can reliably predict which individuals will respond to treatment, either at baseline or after completion of treatment.
4. To determine the trajectory of neural plasticity related to chronic iTBS and cocaine abstinence.
5. To monitor safety of iTBS applied in cocaine dependent individuals.

D. Hypotheses

1. Functional imaging correlates of cue reactivity, reward processing, executive control, and intrinsic network connectivity will differentiate CD and HC participants at baseline.
2. Within the CD group, measures of cue reactivity, reward processing, executive control, and intrinsic network connectivity will be predictive of treatment success and reduction in drug use.
3. Acute iTBS will alter cue reactivity, reward processing, executive control, and intrinsic network connectivity in both CD and HC.

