4. Within the CD group, chronic Active iTBS, relative to Sham, will modulate cue reactivity, reward processing, executive control, and intrinsic network connectivity, which will relate to changes in drug use after the 2-week treatment.
5. Within the CD group, chronic Active iTBS, relative to Sham, will modulate cue reactivity, reward processing, executive control, and intrinsic network connectivity such that neuronal processing in CD participants following iTBS will approximate that in HC (i.e. normalize processes).

E. Experimental Design

Two groups of participants will be recruited: 1) treatment seeking cocaine dependent individuals (CD; n = 90; 45 Active-iTBS and 45 Sham-iTBS); 2) matched community healthy controls (HC; n = 45; within-subject crossover iTBS manipulation). Fifty CD participants in each group will be recruited to obtain the necessary number of participants (n = 30) to complete treatment (see power analysis calculated to ensure necessary power for MRI measures). CD participants may stay in the on-campus inpatient facility approved by the NIDA Clinical Director's office while they participate in this iTBS protocol. The inpatient unit will be available to every CD participant to increase compliance with protocol scheduling. In general, participants will arrive at the inpatient facility the day before their iTBS session. CD participants will be escorted by study staff to and from the inpatient unit on treatment days, which may include automotive pick-up service (e.g., shuttle, taxi). **We will implement a within-subject crossover Active-**

and Sham-iTBS method with the HC participants to provide for the necessary sham control.

[figure not shown]
All participants will receive a post-iTBS nursing assessment and cognitive assessment prior to discharge. An approximate timeline is described below but may vary to account for participant, staff, and facility availability. **All participants, regardless of group, will be scheduled to complete baseline data collection (Characterization; Figures 1 & 2: Visit 1).** An initial scan (Scan 1) will be performed to acquire MRI localization to be used in the iTBS protocol as well as cognitive and affective characterization imaging tasks (week 1); Visit 2 clinical characterization instruments (per protocol 10-DA-N457) and MRI scan (Scan 2; week 1) [participants may be scheduled to complete these characterizations over more than one day, if needed to ensure completion prior to the first iTBS day];

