The double-blind will be preserved by allowing research staff not present during the iTBS session to be responsible for randomizing the active and sham coil. Therefore, research staff present during the iTBS session may be responsible for clinical ratings. The sham coil setting is designed to mimic the auditory artifact and scalp sensations evoked by the real coil without stimulating the brain. The blinded coil has two sides that can be placed on the participant's head; one side active and one side sham. These sides look identical to the researcher and the participant but TMS/iTBS pulses are delivered from only the active side. Which side is facing the participant is determined by the TMS machine or by self-application. The TMS operator will use the coil as set up by the research staff not present ensuring that both the operator and the participant will not know the orientation (active or sham) of the coil. However, in experienced participants, the difference between real and sham iTBS, as well as the difference between different intensities of iTBS is likely to be noticeable. The TMS operator is responsible for verifying the correct iTBS sequence is loaded into the TMS stimulator prior to administering an iTBS session. If a CD participant is randomized to the sham-iTBS group, all iTBS sessions will be sham. Each HC participant will be randomly assigned to either sham- or active-iTBS for visit 3 then crossed over to the other iTBS administration for visit 4. Measurement of motor evoked potentials will be identical between active- and sham-iTBS groups. In an attempt to avoid placebo effects, it is emphasized to the participant that the sensation is related to the stimulation of scalp nerves and muscles, and brain stimulation itself cannot be felt. While our sham stimulation does produce a sensation that is comparably uncomfortable in at least some participants and can produce muscle twitches, it is not qualitatively identical to the active iTBS. Therefore, while efforts are taken to preserve the double-blind, it is possible that the participant and/or the experimenter will become unblinded to the treatment condition. Because of

this, a questionnaire assessing the blind will be administered to the participant (Appendix 46) and the iTBS administrator (Appendix 47). Also, an assessment of pain will be administered to the participant (Appendix 46).

6. Discharge Procedures

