or completed protocols where task reproducibility was not compromised in several of the tasks we will implement here (i.e., Flanker, Stroop, the decision making task, MID, or SSRT). In addition, it should also be noted that participants will receive extensive and repeated training on all tasks throughout the protocol. This training, taking place on multiple days, is expected to help mitigate the impact of in-scanner practice effects on the measures of interest. The presence of a group receiving CM and sham-ITBS will also help control for any practice effects. Nonetheless, potential confound of practice effects will be examined and if observed, may be a potential limitation of the study.

2. Relationship to Other Protocols

All participants in this protocol will first enter the approved NIDA-IRP general screening protocol. Data from the screening protocol will be used to determine eligibility. Every participant in the Expanded Feasibility Study will also be enrolled in protocol 10-DA-N457 to obtain characterization information. Data obtained under the screening protocol and 10-DA-N457 may be shared with this and potentially other protocols.

vi. Statistical Analysis

Behavioral performance measures (e.g., response time, error rate, and hit rate) on each of the cognitive tasks as well as questionnaire data from each of the experimental conditions will be compared both within and between experimental groups using mixed, repeated-measures ANOVA, and linear mixed models. When assessing the statistical results from the behavioral and questionnaire data, a standard α -level of 0.05 will be used. Alpha-levels for multiple comparison follow-up tests will be corrected using an appropriate method (e.g., Bonferroni, Tukey, Scheffe).

Without knowing the final breakdown of completers and non-completers, we cannot definitively outline the planned analyses, but several options are possible. For example, if a substantial number of participants fail to complete 10 iTBS treatment days, this group could be included as a separate group for comparison. Further analyses with this group would depend on the characteristics of the group vis a vis the 10 iTBS treatment

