Endorsing suicidality on the MADRS is an example of a red flag. If a participant endorses this state while the MADRS is administered, a flag is generated, and usually addressed immediately by the clinician administering the MADRS. If a participant reports suicidal thoughts, the CDW Critical Item Alert System will be initiated following the NIDA SOP. Participants may also endorse acute states of depression or mania while participating in this study. Sleep patterns will be tracked to assess potential sleep deprivation. Significant sleep deprivation, or lack of sleep, may have a clinical impact on participants. If this occurs, the LAI will initiate the intervention protocol. This intervention may include referral and/or discharge from the study if clinically significant.

i. Primary Safety Endpoints and Associated Stop Rules

Three outcomes will be monitored throughout the study as safety endpoints associated with a stop rule. As described below, we will track iTBS-induced seizures,

neurocognitive function, and clinically significant adverse events requiring outside evaluation. Chi-square tests will be calculated to test frequency differences between groups (active iTBS vs sham iTBS) for each of these endpoint measures. Each **stop rule** is described in detail below.

1. **Number of iTBS-induced seizures:** more than 1 iTBS-induced seizure resulting in hospitalization within any 10 consecutive participants who receive iTBS will result in a protocol hold until further evaluation by the PI, FDA, and DSMB. The Blind will be broken for any participant with an iTBS-induced seizure. We will also consult [name], M.D., Ph.D., Director, Neuromodulation Program within the Division of Epilepsy and Clinical Neurophysiology, Department of Neurology, Boston's Children's Hospital and Associate Professor of Neurology at Harvard Medical School. [name] is a member of our DSMB and possesses the necessary clinical expertise to evaluate the proposed safety endpoints. No new iTBS sessions will be administered to any participant once this stop rule is enacted until evaluation of the events is concluded and it is deemed appropriate to proceed. However, participants who have completed their iTBS treatments may be scheduled for Contingency Management (CM), MRI scan, or follow-up visits.

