- 1. Clinically significant worsening of cocaine use behavior will be evaluated and monitored as follows:** Although neuroplastic changes in brain activity assessed with fMRI is our primary outcome variable of interest, we will measure cocaine use behavior (Appendices 13: Cocaine use, Pattern, and Withdrawal Questionnaire, & 21 Time-Line Follow back) at baseline and longitudinally throughout the protocol. Among the cocaine use behaviors assessed is maximum dollar amount spent during the longest lifetime binge. Chi-square tests will be calculated to test frequency differences between groups (active iTBS vs sham iTBS) for this endpoint measure. If a participant reports a binge amount in dollars that exceeds 3 X the greatest binge dollar amount, the following steps will be taken:
 - a. The iTBS treatment for this participant will be paused
 - b. The participant will be scheduled to return the next day for further evaluation, which will include reassessment of cocaine use behavior
 - i. If the participant reports continued excessive cocaine binge behavior, the participant will be referred for alternative treatment. The Blind will be broken for this participant at this time.
 - ii. If the participant reports a return to their normal cocaine use pattern, they will be scheduled for further evaluation in about 1 week.
 - c. After about 1 week, cocaine use behavior will be re-assessed.
 - i. If the participant reports further episodes of excessive cocaine binge behavior, the participant will be referred for alternative treatment. The Blind will be broken for this participant at this time.

- ii. If the participant reports a return to their normal cocaine use pattern, they will be allowed to continue in the study. Their treatment schedule will be resumed at this point.

As soon as the increase is noted and at each follow-up visit, the MAI (or covering clinician) will assess precipitants to the change in cocaine use behavior to ascertain whether a significant life-event (e.g., death of a family member) could be related to a spike in cocaine use behavior (vs. the iTBS itself). Detailed evaluation of the situation is necessary to understand the clinical ramifications of continuing, or discontinuing, the iTBS administrations. If, at any point, the MAI (or covering clinician) concludes that iTBS was likely responsible for the change in cocaine use, the participant will not resume iTBS treatments.

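### Safety endpoints are compared only by chi-square, which is undefined for the likeliest seizure result and at low counts can turn on an unstated continuity correction

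*Combined protocol and SAP*

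**What the plan says.** Sections IV.C.i and IX.C.i (Primary Safety Endpoints and Associated Stop Rules) list three monitored outcomes: iTBS-induced seizures, Trails B performance, and clinically significant adverse events. Of all three they say "Chi-square tests will be calculated to test frequency differences between groups (active iTBS vs sham iTBS) for each of these endpoint measures". Sections IV.C.ii and IX.C.ii (Clinical Efficacy Cocaine Use Endpoint) use the same sentence for binge worsening: "Chi-square tests will be calculated to test frequency differences between groups (active iTBS vs sham iTBS) for this endpoint measure".

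These sections do not give an exact alternative, a continuity correction, a confidence interval, an analysis set, a counting unit (participant, treatment day or session) or an alpha. Section III.G.vi says "a standard α -level of 0.05 will be used", but of behavioral and questionnaire data. Its power calculation concerns functional connectivity, not safety.

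The CD sample in III.E is "treatment seeking cocaine dependent individuals (CD; n = 90; 45 Active-iTBS and 45 Sham-iTBS". Healthy controls (HC) have a different design (III.A): "HC participants will be scheduled for 2 DAYS of iTBS and receive 1 DAY of active iTBS", plus one day of sham. Aim 5 in III.C is to monitor the safety of iTBS in cocaine dependent individuals.

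**The concern.** Chi-square relies on a large-sample approximation, conventionally trusted when expected cell counts are at least 5. These endpoints are meant to be rare. If there are no events, the statistic is zero divided by zero. If there are a few, the corrected and uncorrected versions can fall on opposite sides of 0.05, and the choice could be made after the data are seen. Either way, Aim 5 would get no usable answer from the only analysis named, because a p-value alone does not show how large a risk the data still allow.

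**Working it through.** **Inputs.** 45 CD participants per arm (III.E). Sessions per CD participant (III.A): "10 DAYS of iTBS treatment includes a total of 30 iTBS SESSIONS". iTBS seizures: 1 in 16,952 sessions, shown as .06 per 1000 (Table 2, III.G.iv). Two-sided 0.05 is my assumption. III.E and III.G.vi also mention 50 per arm or 100 CD participants. I use 45; 50 would change little.

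**Plan's own figure.** 1 / 16,952 × 1000 = 0.059, which agrees with the printed .06.

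**Seizures.**
- Active CD sessions: 45 × 30 = 1,350.
- Expected seizures in the active arm: 1,350 × 0.06 / 1000 = 0.08.
- Expected count per arm under equal risk: 0.08 / 2 = 0.04, taking none from sham.
- Chance of no seizure in the active arm: exp(−0.081) = 0.92.
- At the upper 95% limit for 1 in 16,952 (0.33 per 1000), 0.44 seizures are expected, or 0.22 per cell.

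**Other endpoints.** With equal arms, the expected event cell is (total events) / 2. Reaching 5 needs 10 events: 10 / 90 = 11.1% of CD participants, or 10 / 60 = 16.7% of completers. The documents give no rates. As an indication only, if events were independent at 11.1%, a rule of more than 1 event in any 10 consecutive participants would trigger with about 99% probability over 90 participants. At 5% it is 71%, and at 2% it is 22%. The hold rules thus sit naturally with lower rates, though they do not prove them.

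**Effect of the choice of test, 4 v 0 of 45.** The table is 4, 41 / 0, 45, so ad − bc = 180 and the product of the margins is 45 × 45 × 4 × 86 = 696,600.
- Pearson: 90 × 180² / 696,600 = 4.19, p = 0.041.
- Yates: 90 × (180 − 45)² / 696,600 = 2.35, p = 0.125.
- Fisher: 2 × C(45,4) / C(90,4) = 2 × 148,995 / 2,555,190 = 0.117.

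| Events (of 45 v 45) | Pearson | Yates | Fisher | Boschloo |
|---|---|---|---|---|
| 4 v 0 | 0.041 | 0.125 | 0.117 | 0.073 |
| 6 v 1 | 0.049 | 0.115 | 0.110 | 0.073 |

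**True size of uncorrected Pearson at 45 per arm**, enumerated over all tables: 0.1% at an event rate of 1%, 1.0% at 2%, 4.9% at 5%, and a peak of about 6.0% near 8%.

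**Power for 10% v 2%**, same enumeration: Pearson 39%, Boschloo about 26%, Fisher 15%.

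**What zero events would allow.** The exact two-sided 95% upper limit for 0/45 is 1 − 0.025^(1/45) = 7.9%. For 30 completers it is 1 − 0.025^(1/30) = 11.6%.

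**The case against.** **Healthy controls.** A reader might infer that HC are counted in both columns, because each receives both conditions and the seizure hold covers all participants who receive iTBS. No section says so, and the text points to the CD arms. Aim 5 names cocaine dependent individuals. III.G.iii.5 uses the term sham-iTBS group for CD randomisation. The same group wording is applied to a cocaine-binge endpoint that does not fit HC. What stands is that the analysis set is unstated. Pooling HC would break independence and mix 3 active sessions with 30.

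**False positives.** The p-value differences above might suggest that chi-square over-declares harm. It does not to any material degree: its size is at most about one percentage point over nominal, and far below nominal for very rare events. If the Yates version is meant, it nearly matches Fisher.

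**Low counts everywhere.** These are documented only for seizures. A Trails B time over 90 seconds is checked after every treatment day and could be common. A second event in 10 participants leads to a hold pending evaluation, not to termination, and the adverse-event rule also requires similar clinical features. Events can therefore accumulate.

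**Safety decisions do not use these tests.** This is correct. They rest on the hold rules, clinician evaluation and DSMB review, and no section treats a non-significant chi-square as evidence of safety. A limit of 7.9% for 0/45 comes from the sample size, whatever the test.

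**Exact tests cost power to detect harm.** This is true, and for a safety comparison it matters. It argues for intervals as the main result, not for keeping an unspecified chi-square.

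**Conclusion.** The point holds in a limited form. For seizures, the only named test will most likely be undefined: 0.08 events are expected in the active arm, with about a 92% chance of none there. This assumes that Table 2's rate carries over to cocaine users and that sham causes no seizures; at the upper limit of that rate the expected count is still 0.22 per cell. For the other endpoints, any total of 9 or fewer events in 90 CD participants falls below the conventional range, and the conclusion can then hinge on the unstated correction.

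The documents do not support the stronger claims that HC are double-counted, that all endpoints have tiny counts, or that type I error is badly inflated. Participant protection is not affected. What is missing is a pre-specified analysis that answers Aim 5.

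**What to change.** In IV.C.i, IV.C.ii, IX.C.i and IX.C.ii, replace the chi-square sentence with the following:

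1. Compare the randomised CD arms among everyone who received at least one session, stating whether the orientation exposure counts as one.
2. Count each participant once per endpoint (at least one event or none).
3. As the main result, report each arm's risk and the risk difference with exact 95% confidence intervals, naming the methods (for example Clopper–Pearson for each arm and an unconditional exact interval for the difference).
4. Name one unconditional exact test, Boschloo's, as secondary, with its alpha.
5. Report HC events separately by condition, as paired data.

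The cost is wording only, with no new data and no change to the hold rules. The downside should be stated: nominal power for 10% v 2% falls from 39% with uncorrected Pearson to about 26% with Boschloo (Fisher would give 15%). For that reason the intervals, not the p-value, should carry the safety conclusion.
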